### **Specific Objectives**

1. To evaluate the effect of scaling up targeted MTTT/home-based treatment on malaria parasitaemia and hospital consultations and admissions.
2. To determine the prevalence of asymptomatic parasitaemia among afebrile participants.
3. To reduce the burden of malaria in the participating communities.
4. To document challenges which hinder the scale up of mass testing, treatment and tracking of malaria in Ghana.
5. To conduct a cost benefit analysis of the intervention in the area.

### **Study Design:**

This is an Implementation Research (IR) with a longitudinal cohort design to be undertaken within a two year frame work. The interventions are designed to compare the baseline to evaluation findings following the modified protocol of (Ahorlu et al., 2011). **There are two components to this implementation study a). The longitudinal (cohort) study: This is basically the prevalence surveys to be conducted with the selected cohort of children 6 months to 15 years – at baseline and before each of the subsequent MTTT rounds. b). The Survey involves using structured questionnaire to interview caretakers of children under five to solicit their views on the implementation process perceived benefits and challenges etc.** Though the target group is children from 6 months to 15 years of age, all parasitised adults will be cleared of the parasite during the interventions as well to reduce the parasite reservoirs. **Prevalence of malaria**

**trends in cohort group over the study period will reveal the effect of MTTT scale-up on the children 6month to 15 years.** Between interventions, the teams will conduct homes-based management of malaria for all febrile cases confirmed to be positive for malaria parasites. The challenges faced by the implementation team will be documented at every stage and discussed with all the stakeholders at every stage of the implementation.

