Implementation of rapid scale-up preventive interventions in the past decade has led to a reasonable decrease in the burden of the malaria (WHO 2011) especially given the introduction of the WHO policy of test, treat and track (T3) (WHO 2012). The challenges involved with translating research scenarios into implementation are enormous. It is important to understand the bottlenecks that hinder this process in order to undertake mass testing, treatment and tracking in a large scale using existing health systems, especially in an era when global funding for health services is slowing down (Rao et al. 2013).

Any effective control strategy that interrupts the link between man, the parasite and the vector could seriously reduce the transmission of malaria. In this light, interventions focused on clearing of the parasites in asymptomatic individuals in combination with intensive use of other control measures could pave the way for pre-elimination of the parasite in endemic communities (Bousema et al. 2014). This study aims at reducing the asymptomatic parasitaemia in the Pakro sub district of the Eastern Region of Ghana by conducting MTTT for malaria parasitaemia among household members of age 6 months and older and carrying out targeted treatment of all cases with confirmed asymptomatic parasitaemia or clinical malaria. These interventions intend to follow up enrolled participants over a period of two years. Hospital records will also be studied to document trends in malaria admissions and occurrence of other diseases in the area before and after the interventions.

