### **Main objective**

The main objective of this study is to explore the impact of scaling up mass testing, treatment and tracking on malaria prevalence among children under fifteen years of age in the Pakro sub district of Ghana.

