### **Study participants**

Community entry activities to sensitise the chiefs and the general population will be conducted at the beginning of the study through meetings and durbars (Ansah et al., 2015; Ahorlu, et al., 2009). Once the community leaders and the population have accepted the project, the household will be numbered and participants per household will be registered during a household census. All households will be given a unique identification code. Each individual within the household will be assigned a code that links them to a particular household and community. After obtaining consent from the household heads, the children will be enrolled but individual assent and consent will be obtained from the other adolescents and adults in the household. **A cohort of 460 children age 6 months to 15 years will be selected and enrolled into the longitudinal study which will consist of prevalence surveys undertaken before each MTTT. Caregivers of the children in the cohort will be enrolled for the community surveys using questionnaires. In this implementation research the entire population of the seven selected communities will be tested, treated and tracked. This is intended to clear the parasite pool in the community.**

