#### **Intermittent preventive treatment for the household members**

The research team **together with Community assistants/volunteers** will conduct **house-to-house** testing (using RDTs) of all children (from 6 months old) and adults residing in 7 selected communities for the presence of malaria parasites. **For this study, the investigators will use the Ag P.f RDT which detects histidinie-rich proteins II antigens (HRP-2 Ag) specific to *P.falciparum* in human blood. The RDTs will be supplied by the Ghana Health service through the National malaria control programme which uses the services of WHO-FIND Lot Testing Programme for quality assurance. Thus, the investigators are using the same RDT that has been procured by the NMCP and are being used routinely in Ghana.** To enable follow up studies in a case where treatment failure is reported, 200ul (two drops) of blood will be collected on filter paper. This will be used to determine immunological parameters such as antibody levels to specific antigens using Polymerase Chain Reaction (PCR) and Enzyme Linked Immunosorbent Assay (ELISA). **RDT confirmed cases who are treated but presents persistent malaria related symptoms such as fever on day 7 will be tested using microscopy and to determine clinical failure. This study is not designed to test for parasite**

**resistance to drug (drug efficacy) and the Project clinicians will advise on the next line of action.** This could be taken up by a masters' student. **However, the student will need to submit a different protocol to the ERC for approval.** All participants confirmed (**using RDTs**) to be carrying the malaria parasite will be treated using ACTs following the Ghana National Malaria Treatment Guidelines and followed up **on days 1, 2, 3 during treatment as DOTs (Directly observed therapy) and on day 7 post treatment.** The research team together with **Community volunteers will be provided the treatment guidelines which specify the dosage for each treatment regimen.** Participants who receive the treatment will be observed for five minutes to ensure that they retain the drug. Those who vomit within this period will have the treatment repeated.

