### **Sample size**

This is an implementation study aimed at enrolling an entire population estimated at 4500 participants from the 7 selected communities in Pakro sub district. This population was obtained following data from a head count in preparation for the mass distribution of LLIN in 2016 - Abase newsite = 800, Fante town = 1450, Adjenase/Kwettey = 1102, Piem/Odumsisi = 323, Adesa/Nsuablaaso = 480, Sacchi/Tabnkro = 201, Odumtokro = 129 (Pakro Health Centre records). However, since the target effect of this intervention is focused at the children age 6 months to 15 years, a community survey with a sample of 368 children will be needed to determine the malaria prevalence projected at 50% in the study population. This has been determined using the formula of Yamane where  $n = N/[1+N(e)^2]$  (Israel 1992) considering a 95% confident level (CI) and  $\pm 5\%$  precision. Assuming a loss to follow up of 10% and a non-response rate of 10%, the sample size is readjusted to 460 children calculated from  $(38/1-0.2)$  for the community survey. At evaluation the available sample size will be determined. This is the group for which questionnaires will be administered. Following a census of the households, children under 6 months to 15 years old will be **randomly selected for the longitudinal cohort study, they will then be** divided into the various age groups 6 months to 11 months, 1-4 years, 5 -10 years and 11-15 years. For each age group the investigators will randomly select 116 children.

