### **Problems Anticipated**

It is anticipated that ACTs and RDTs supplies could delay. In order to avoid this, the investigators have approached the national malaria control programme to arrange for drugs and RDTs supply through the Eastern Regional Store. The investigators anticipate the number allocated to houses in the communities could be wiped and so the investigators have each house data linked to the name of the house. This could enable us to trace the participants easily. In the field the investigators will use forms that already carry the names of the families following the census. Names of new people could be added.

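### The cohort meant to show the MTTT effect on children 6 months to 15 years is drawn once, and by Survey 6 it contains no child under about 2 years

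*Protocol*

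**What the plan says.** The protocol declares a longitudinal cohort design. Under Study Design, malaria prevalence "trends in cohort group over the study period will reveal the effect of MTTT scale-up on the children 6month to 15 years". The cohort is described as follows.

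- **Selection.** Under Study participants: "A cohort of 460 children age 6 months to 15 years will be selected and enrolled into the longitudinal study". Under Sample size, children are drawn after the household census and "divided into the various age groups 6 months to 11 months, 1-4 years, 5 -10 years and 11-15 years"; then "For each age group the investigators will randomly select 116 children".
- **Follow-up.** Under Introduction/Rationale: "These interventions intend to follow up enrolled participants over a period of two years". Sample size adds only that the number available will be established at evaluation. No top-up, rotation or re-draw is mentioned. Problems Anticipated says "Names of new people could be added", but this concerns the household field forms, not the cohort.
- **Dates.** The Work Plan puts Survey 1 in April to July 2017 and Survey 6 in November 2018 to February 2019.

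Alongside the cohort, each round includes "testing (using RDTs) of all children (from 6 months old) and adults residing in 7 selected communities". Exclusion criteria confirms that anyone present at a survey is tested.

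The population for the effect varies. The Main objective refers to "malaria prevalence among children under fifteen years of age in the Pakro sub district of Ghana", Study Design to the cohort aged 6 months to 15 years, and Data Management and Analysis to the area. The Work Plan refers to children and adults, with a milestone for the whole sub-district.

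**The concern.** A cohort drawn once grows older. If its trend is the evidence for an effect on children aged 6 months to 15 years, the group observed at the end is no longer that group: the youngest ages have gone and some of the oldest have passed the limit. Two things follow.

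- **Coverage.** The final surveys say nothing about the youngest children in the target range. Age adjustment cannot restore ages that the cohort no longer contains.
- **Confounding with age.** An unadjusted comparison of baseline with evaluation in the same children combines the MTTT effect with 19 months of ageing. The protocol's own Introduction says that age matters greatly to the malaria burden and that parasitaemia begins to fall after age 5.

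The source of the effect estimate is fixed in the protocol, so this is not merely a detail that an analysis plan would supply.

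**Working it through.** **The plan's own figure.** Yamane with N = 4,500 and e = 0.05 gives 4,500 / (1 + 4,500 × 0.0025) = 4,500 / 12.25 = 367.3, rounded up to 368. Then 368 / (1 − 0.2) = 460, as stated (the 38 in the printed formula is evidently 368). Four bands of 116 make 464. The sample size is not in question here.

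**Elapsed time, Survey 1 to Survey 6**

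- Work Plan windows: April 2017 to November 2018 = 19 months; July 2017 to February 2019 = 19 months.
- Individual child: shortest July 2017 to November 2018 = 16; longest April 2017 to February 2019 = 22.
- Quarterly spacing (Timely treatment section; Explanation of Budget): 5 intervals × 3 = 15.
- Four-monthly spacing (Personnel, Intervention): 5 × 4 = 20.

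**Youngest child at Survey 6.** 6 + 19 = 25 months. The full range is 6 + 15 = 21 to 6 + 22 = 28 months.

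**Lower bands, ages assumed uniform within each band**

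- 6-11 months: 116 at baseline, 0 at Survey 6 on every spacing. By the Work Plan windows the band is already empty at Survey 4 (from February 2018), at least 6 months after Survey 1 closes.
- Under 2 years: 116 + 116 × 12/48 = 145 of 464 (31%) at baseline, 0 after 19 months. After 15 months, 116 × 3/6 = 58 remain, aged 21 to 23 months; after 16 months, 116 × 2/6 = 39.

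**Top band**

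- If it runs to the 16th birthday (60 months wide): 116 × 19/60 = 37 have passed it (31 to 43 over 16 to 22 months); the oldest is (192 + 19)/12 = 17.6 years.
- If it ends at the 15th birthday (48 months wide): 116 × 19/48 = 46 have passed it (39 to 53); the oldest is (180 + 19)/12 = 16.6 years.

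**Share of the target age range uncovered, ages assumed uniform over the whole range**

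- To the 16th birthday: 19/186 = 10.2% (16/186 = 8.6% to 22/186 = 11.8%).
- To the 15th birthday: 19/174 = 10.9% (9.2% to 12.6%).
- At 15 months' spacing: 15/186 = 8.1% or 15/174 = 8.6%.

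The infant band is 25% of the cohort only because it is oversampled; it spans 6/186 = 3% of the age range.

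**Direction of the ageing effect.** The document gives no age-specific prevalence for this area, so two invented age curves were tried with no MTTT effect and 19 months of ageing. With 50% up to age 5, then falling to 35% at 11 and 25% at 16, the cohort mean moves from 43.1% to 41.1%. With a rise from 10% at 6 months to 25% at 12 months and 58% at 5 to 11 years, then a fall to 50% at 16, it moves from 42.7% to 49.2%. The sign depends on the curve assumed.

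**The case against.** The strongest reply is that closed follow-up is deliberate. The Inclusion criteria require residence for the study period, and the Exclusion criteria bar short-stay children. Every closed cohort ages, and the effect statement can be read as concerning children enrolled at those ages. That is a legitimate question, which is why the cohort should stay. But the protocol does not say that this is what it means.

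A second reply is that all residents are tested anyway, that Data Management and Analysis stratifies by age and compares prevalence in the area, and that age adjustment belongs in an analysis plan. This stands in part: the data will exist. But that section does not say its comparison uses all residents, while Study Design names the cohort.

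Third, the age break that the Introduction names, around 5 years, stays well populated: children under five go from 232 (50%) to 116 + 116 × 29/48 = 186 (40%). This stands.

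Four stronger readings are not supported.

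- **That ageing materially distorts the effect.** Neither its size nor its sign can be derived. Beside the 50% to 10% fall assumed in the budget's Treatment section, it is probably small.
- **That 17-23% of target children are uncovered.** This combines the budget's 30% under-five share with an assumed 45-60% of residents under 16. It implies 1,350/5 = 270 children per year of age below five but only 675/11 = 61 (at 45%) or 1,350/11 = 123 (at 60%) above, an implausible drop.
- **That exactly 19 months is settled.** The stated schedules conflict, and the Work Plan also lists an evaluation in January to July 2019 without saying whether it is a further survey.
- **That all-resident data should replace the cohort.** The cohort is a random sample surveyed before each round; the campaign results are gathered with volunteers and coverage will vary. Neither is plainly better alone.

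**Conclusion.** The point holds as a mismatch between the stated target group and the group observed, and it should be corrected. On any stated schedule, the 6-11 month band is empty at Survey 6, the youngest cohort child is about 2 years old and the top of the age range is exceeded. About 10% of the target range (9-13% by the Work Plan windows, about 8% at the shortest spacing) goes uncovered. A younger age structure would raise that share by an amount the document does not fix.

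This rests on two assumptions: that the cohort is drawn once, inferred from the described selection and the absence of any refill rule, and that ages are uniform within bands and, for the uncovered share, across the range. The main loss is evidence on the youngest children. Mixing of MTTT with ageing is a secondary matter of unknown sign.

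**What to change.** - **Study Design.** Keep the closed cohort for within-child change and haemoglobin. State that it speaks for children enrolled at 6 months to 15 years, and adjust its baseline-to-evaluation contrast for age at survey. Baseline and Survey 6 ages overlap only from about 25 months to the upper limit, so adjustment outside that range is extrapolation.
- **Data Management and Analysis.** Add an estimate for children aged 6 months to 15 years at the time of each round, from the RDT results of all resident children tested, standardised to the baseline census age distribution. Report coverage (tested over census-eligible) at each round, and a version limited to children registered at the baseline census, so the influence of newcomers is visible.
- **Consistency.** Use one age range and one area in the Main objective, Study Design, Data Management and Analysis, and Work Plan. Reconcile the survey spacing across the Timely treatment section, the Work Plan and the two budget passages.

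**Cost.** No extra testing is needed through Survey 6: 5,000 RDTs per round are planned for 4,500 residents over six rounds, and individual codes are already assigned. A separate 2019 evaluation survey is not costed. Data entry and analysis grow. The cohort yields 460 × 6 = 2,760 results. If 40-60% of residents are in the age range (an assumption), full coverage would yield 1,800 to 2,700 per round, or 10,800 to 16,200 over six, within 20 budgeted statistician days. Coverage will vary by round, and later births and in-migrants will have been exposed to fewer rounds.

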## **Methodology**

### **Study Area**

Pakro is one of five sub-districts in the Akwapim south district health directorate (DHD) in the Eastern region of Ghana (DHD, 2014). The Akwapim south district lies within the semi-equatorial climatic region, and experiences two rainfall seasons in a year, with an average rainfall of 125cm to 200cm. The first rainy season begins from May to June with the heaviest rainfall in June, whilst the second rainy season begins from September to October. According to the Ghana Statistical Service (GSS), the average household size in the Akwapim South district is estimated to be 4.0 whilst the average number of households per house or compound is estimated to be 1.6 (GSS, 2010). The Pakro sub-district has an estimated population of 7,889, and is bounded to the east by Akwapim North district; to the north by Ayensuano district; and to the west by Nsawam Adoagyiri Municipality. The sub-district is made up of 22 communities, and has 3 health care facilities (1 Health Centre and 2 Community-Based Health Planning Service (CHPS) compounds) (DHD, 2014). Due to limited resources, only seven communities will be selected for this study. This include Abeasi Newsite, Fante Town, Zongo (Adjenase/Kweitey), Piem/odumsisi, Adesa Latebibio, Sacchi/Tabankro and Odum Tokuro. These are communities with a relatively high population density. The Pakro Health Centre is one of thirty sentinel sites monitoring malaria prevalence in the country coordinated by the Noguchi Memorial Institute for Medical Research (NMIMR). Malaria parasite positivity rate was estimated to be 45.7% in 2014 (DHD, 2014). In the same year anaemia among pregnant women at 36 weeks of gestation was 21% (DHD, 2014).

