### ***Expected Outcome/Results***

1. The effect of scaling up targeted MTTT/home-based management on hospital admissions will be understood.
2. The prevalence of asymptomatic malaria parasitaemia among afebrile children aged 6 months to 15 years and adults in the Pakro sub district will be known.
3. Reduced burden of malaria in the participating communities
4. Document challenges that hinder the scale up of mass testing, treatment and tracking of malaria in Ghana.
5. The cost benefit analysis of the scaling up MTTT intervention in the area will be known.

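### The protocol promises prevalence and effect for the Pakro sub-district, but its design supports estimates only for the seven communities it covers

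*Protocol*

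**What the plan says.** **Coverage.** The Study Area section states "The sub-district is made up of 22 communities" and "The Pakro sub-district has an estimated population of 7,889". It continues: "Due to limited resources, only seven communities will be selected for this study". The seven are then named, followed by the remark "These are communities with a relatively high population density". The sections on study participants and on treatment of household members confine testing and treatment to these seven. The Sample size section speaks of "enrolling an entire population estimated at 4500 participants from the 7 selected communities in Pakro sub district" and attaches its assumed 50% prevalence to the study population.

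**Claims made for the sub-district.** Expected Outcome/Results, item 2, says that prevalence "among afebrile children aged 6 months to 15 years and adults in the Pakro sub district will be known". The primary row of the Work Plan repeats this. The milestone beside it promises publications showing the intervention's effect on prevalence in the sub-district. The Main objective concerns the impact "on malaria prevalence among children under fifteen years of age in the Pakro sub district of Ghana", which can be read the same way. The hypothesis in the Project Summary and the Rationale is also placed in the sub-district.

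**Narrower claims elsewhere.** Specific Objectives 2 and 3 refer to participants and to participating communities.

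**The concern.** A reader of the expected results or the primary outcome row would take the reported prevalence, and any fall in it, to describe all 22 communities. Residents outside the seven are neither tested nor treated, and the protocol gives no sampling, weighting or assumption that would link them to the seven. No later analysis can supply that link, because no prevalence data are planned from those communities.

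At stake is what the trial may conclude. The protocol expects its findings to inform decisions on national scale-up, so the population they describe should be stated correctly.

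**Working it through.** **Inputs.** Sub-district: 22 communities and 7,889 residents (Study Area, where the figures are given with the 2014 district report). Seven communities: 4,500 residents in round figures (Sample size, from a head count for the 2016 net distribution). Precision of 5 points, loss to follow-up of 10% and non-response of 10% (Sample size).

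**1. Which population does the sample size target?** The protocol uses n = N/(1 + N·e²) with e = 0.05.
- N = 4,500: 4,500/(1 + 11.25) = 367.3, rounded up to 368. This is the stated figure.
- Inflation: 368/(1 − 0.20) = 460. This is also the stated figure.
- N = 7,889: 7,889/(1 + 19.72) = 380.7, rounded up to 381. This does not match.

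The stated sample size is therefore reproduced with the seven communities as the population, not with the sub-district.

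**2. Share covered.**
- Listed head counts: 800 + 1,450 + 1,102 + 323 + 480 + 201 + 129 = 4,485.
- 4,485/7,889 = 56.9%; with the rounded 4,500, 57.0%.
- Not covered: about 43%, in 22 − 7 = 15 communities.

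**3. What this could do to a sub-district prevalence.** If the seven-community figure is presented as the sub-district figure, the shift is (share not covered) × (difference in prevalence between unselected and selected communities). The protocol gives no value for that difference, so the values below are assumptions:

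| Assumed difference (points) | Shift in sub-district figure (points) |
|---|---|
| 10 | 0.43 × 10 = 4.3 |
| 20 | 0.43 × 20 = 8.6 |
| 30 | 0.43 × 30 = 12.9 |

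The shift can go either way. With 50% in the seven and nothing assumed about the rest, the sub-district value could lie anywhere from 0.57 × 50 = 28.5% to 28.5 + 43.0 = 71.5%.

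**4. Would a larger sample help?** No. With N = 7,889 the formula gives 381, and 381/0.8 = 476.25, rounded up to 477. Children in the 15 unselected communities would still have no chance of selection.

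**The case against.** The strongest reply is that the operative text is already narrow. The Study Area section openly says that seven of 22 communities are taken and why. The design section reads the effect from trends in the cohort, and the sample size is built on the seven. Naming the sub-district may simply give the location, as it plainly does in the Sample size section. That is fair for the Main objective, which is weak support on its own. It does not cover item 2 of the expected results or the Work Plan's primary row and milestone, which say what will be known or shown about the sub-district itself.

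Several stronger readings are tempting but unsupported:

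- *The planned ±5% precision is false for the sub-district.* The protocol states that precision for the study population only, and step 1 of the working confirms it.
- *The communities were chosen for density, so prevalence is biased in a known direction.* Limited resources are the stated reason; density is a description that follows the list. Nothing in the document links density to prevalence. Two of the seven, with 201 and 129 people, are smaller than the average of the rest, (7,889 − 4,485)/15 = about 227, although head count is not density.
- *The sub-district effect is about 57% of the effect seen.* Using the 10% prevalence projected in the budget for the later rounds, and holding the rest at 50%, the sub-district would stand at 0.57 × 10 + 0.43 × 50 = about 27%. This assumes no change at all over two years in communities that nobody observes, and so no spillover, secular trend or other control activity. It is not an estimate that the trial could report.

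The 43% is also approximate. The two totals come from different sources and years, several of the seven carry paired names, so the count of 15 depends on how the 22 were counted, and both totals cover all ages whereas the main objective concerns children.

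**Conclusion.** The point stands as a contradiction about the target population. The expected results and the Work Plan claim the sub-district; the sampling frame, the intervention and the Specific Objectives cover seven communities holding roughly 57% of its residents. For those seven the point raises no objection to estimating prevalence, and it would be wrong to infer that the design cannot deliver it there. For the sub-district, the size and direction of any error cannot be determined from the document. The 4 to 13 point range rests entirely on an assumed 10 to 30 point difference in the unselected communities. The consequence is limited to what may be concluded: no procedure, sample size or comparison changes.

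**What to change.** In the Main objective, item 2 of Expected Outcome/Results, the primary row and milestone of the Work Plan, and the hypothesis in the Project Summary and Rationale, replace *in the Pakro sub district* with *in the seven selected communities of the Pakro sub district*. Add one sentence saying that the communities were not chosen at random and that results do not extend to the others without further assumptions. Do not report a sub-district effect obtained by scaling with the population share, because the untreated communities are not observed.

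The hypothesis also compares survey findings with hospital records. The section on extracting those records does not restrict them to residents of the seven, so the reworded hypothesis should say which population the records cover.

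The sample size of 368, inflated to 460, stays as it is. The cost is a wording amendment and a narrower claim. If the sub-district must remain the target, communities would have to be sampled at random from the 22 for the prevalence estimate, which needs resources that the protocol says are limited.
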